6.13.2.2. Severe Persistent Hyperglycemia

A summary of initiation of rescue therapy in response to severe, persistent hyperglycemia will be provided by treatment. If there are sufficient number of episodes (≥ 10), time-to-first-event analyses for the initiation of rescue therapy will be conducted by treatment using a cox proportional regression model. For patients without event “time-to-event”, event time will be censored at end of treatment period. A listing of patients who initiated rescue therapy will be provided.

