7.8.2.3. Management of Patients with Severe, Persistent Hyperglycemia during the Treatment Period

Severe, persistent hyperglycemia will be collected during the trial to assess the risk of extreme imbalance in glycemic control.

Investigators will be trained on the application of criteria for deciding when and how to intervene with patients who do not reach glycemic targets. If any of the FBG values within 1 week for 2 consecutive weeks exceed the limits outlined below and no intercurrent cause of the hyperglycemia could be identified (investigators should first confirm that the patient is fully compliant with the assigned therapeutic regimen and that he or she does not have an acute condition causing severe hyperglycemia), rescue medication will be prescribed as an add-on to randomized treatment. Patients will continue to follow the protocol-specified visit schedule as described in Section 7.4.2.

- >270 mg/dL (>15.0 mmol/L) from baseline to Week 6 (4 values/week)
- >240 mg/dL (>13.3 mmol/L) from Week 6 to Week 12 (4 values/week)
- >200 mg/dL (>11.1 mmol/L) from Week 12 to end of trial (4 values/week)
OR
- HbA1c \geq 8.5% (\geq 69 mmol/mol) by and after Week 24

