- country,
- any past prior use (yes or no) of any oral antidiabetic medication,
- baseline HbA1c category [$\leq 8.5\% (\leq 69 \text{ mmol/mol})$ or $> 8.5\% (> 69 \text{ mmol/mol})$],
- and baseline measurement as a covariate.

For analyses with HbA1c, the baseline HbA1c category will not be included in the model. An unstructured covariance structure will model the relationship of within-patient errors.

The Kaplan-Meier method will be used for estimation of cumulative event-free survival rates over time, and cox proportional hazards regression analysis will be used to compare hazard rates among treatments.

Summary statistics for categorical measures (including categorized continuous measures) will include sample size, frequency, and percentages. Fisher's exact test will be used to examine the treatment difference in categorical outcomes. Logistic regression may be used to examine the treatment difference in binary efficacy outcomes. The negative binomial regression model will be used for the treatment comparison of discrete count measures if deemed appropriate.

Other statistical methods may be used, as appropriate, and details will be documented in the SAP.

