5.2. Method of Assignment to Treatment

Around 472 patients who meet all criteria for enrollment will be randomized to 1 of the study treatment arms at Visit 3. Assignment to treatment arms will be determined by a computer-generated random sequence using an interactive web-response system (IWRS). Patients will be randomized in a 1:1:1:1 ratio to receive 5 mg tirzepatide, 10 mg tirzepatide, 15 mg tirzepatide, or placebo. The randomization will be stratified by country, baseline HbA1c concentration ($\leq 8.5\%$, $>8.5\% [\leq 69, >69 \text{ mmol/mol}]$), and past prior use of oral antidiabetic medication (OAM) (Yes or No).

6. A Priori Statistical Methods

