6.3. Adjustments for Covariates

The study is stratified by country, baseline HbA1c ($\leq 8.5\%$, $>8.5\% [≤69, >69 \text{ mmol/mol}]$), and past OAM use (Yes or No). Where necessary to be included as a stratification factor, countries with fewer than 10 randomized patients will be pooled into 1 category (pooled country). For HbA1c related analyses, the pooled country and past OAM use will be used as stratification factors and baseline HbA1c as a covariate. For other efficacy analyses, the pooled country, baseline HbA1c ($\leq 8.5\%$, $>8.5\% [≤69, >69 \text{ mmol/mol}]$), and past OAM use (Yes or No) will be used as stratification factors and respective baseline value as a covariate. Stratification factors will be based on the information collected in clinical database.

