6.13. Safety Analysis

Unless specified otherwise, safety assessments will be based on the SS (see [Table GPGK.6.1](#)). All events that occur between the date of first dose of study drug to the date of patient's safety

follow-up visit or patient's end of study participation will be included. For assessing benefit and risk profile through 40-weeks, selected safety analyses may be conducted by utilizing safety data from first dose through the date of 40-week visit. For rare events (<10 patients have the events), summary tables may not be generated, and individual patient level data will be listed.

Unless specified otherwise, comparisons of tirzepatide doses to placebo will be performed.

For selected continuous safety parameters, difference among treatment mean change from baseline at scheduled visits will be assessed via a MMRM using REML. The model will include country/pooled country, baseline HbA1c ($\leq 8.5\%$, $>8.5\% [\leq 69, >69 \text{ mmol/mol}]$), past OAM use (Yes or No), treatment group, visit, and treatment-by-visit interaction as fixed effects, and baseline value of the safety parameter as a covariate. To model the covariance structure within patients, the unstructured covariance matrix will be used. If this model fails to converge, the covariance structures specified in Section 6.12.1.1 will be tested in order.

For selected safety parameters, time-to-first-event analysis via cox-proportional hazards model may be conducted. For patients experiencing an event, "time-to-first-event" will be the time (in weeks) to the first occurrence of the event. For patients without the event, "time-to-event" will be censored at end of study participation (study discontinuation, safety follow-up visit, or date of death).

Where specified, rate of events will be analyzed using a generalized linear mixed-effects model assuming the number of events follow a negative binomial distribution, and with treatment as a fixed effect. The logarithm of years in specified time interval will be adjusted as an offset to account for possible unequal treatment duration in specified time interval between patients.

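### The Cox model for time to rescue names no stratum; stratifying it by baseline HbA1c category, a randomisation factor, would cost nothing and recover some power if that factor strongly predicts rescue (minor)

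*SAP*

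**What the plan says.** Time to initiation of rescue therapy is a safety objective (Protocol section 4, SAP 4.4). Provided there are at least ten episodes, SAP 6.13.2.2 states that "time-to-first-event analyses for the initiation of rescue therapy will be conducted by treatment using a cox proportional regression model". For patients without the event, "event time will be censored at end of treatment period". No covariate or stratum is named.

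The general texts do not fill the gap:

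- SAP 6.13 says of selected safety parameters that "time-to-first-event analysis via cox-proportional hazards model may be conducted", again with no adjustment terms.
- Protocol 10.3.1 says only that "cox proportional hazards regression analysis will be used to compare hazard rates among treatments".
- SAP 6.3 assigns the stratification factors to HbA1c-related analyses and then continues: "For other efficacy analyses, the pooled country, baseline HbA1c" category and past OAM use. It does not mention safety analyses.

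On design, SAP 5.2 states: "The randomization will be stratified by country, baseline HbA1c concentration" (cut at 8.5%) and past OAM use. Protocol 7.8.2.3 gives two routes to rescue. One is a set of fasting glucose limits that apply from baseline and tighten at Weeks 6 and 12. The other is HbA1c ≥8.5% "by and after Week 24".

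**The concern.** Baseline HbA1c category is a factor the trial randomises by and a plausible predictor of this event: a patient who enters above 8.5% and does not improve meets the HbA1c route at Week 24. Several neighbouring safety models do carry the stratification factors: the MMRM for continuous parameters (SAP 6.13), the hypoglycemia models (6.13.2.1), the pancreatic enzyme MMRM (6.13.2.3.1) and the vital signs MMRM (6.13.3). The rescue model, whose event is itself glycemic, does not, and no reason is given.

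Two consequences follow if the factor is strongly prognostic. First, hazard ratios are non-collapsible, so with a true treatment effect the treatment-only HR is closer to 1 than the HR within a stratum. Second, balancing the arms on the factor reduces the true sampling variation of the treatment-only estimate, but its model standard error does not take account of that balance. The test then rejects less often than its nominal level. At stake is the precision of a safety comparison, not any confirmatory conclusion.

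**Working it through.** **The plan's own figures.** The documents give no power, HR or event count for time to rescue. The only power statement (Protocol 10.1) concerns HbA1c, and it reproduces: SE = 1.1 × √(1/88.5 + 1/76.7) = 0.172, 0.65/0.172 ≈ 3.79, less 2.39 for two-sided 0.017, giving 91.9% against at least 90%. It does not bear on this analysis. The sizes below therefore rest on assumptions.

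**Inputs from the documents:** 118 per arm; 40 weeks; stratification at 8.5%. Up to 35% of placebo patients are assumed to start rescue or stop treatment, which caps plausible placebo rescue.

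**Assumed inputs:** 40-week placebo rescue risk in each stratum, share of patients above 8.5%, treatment HR, constant hazards.

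**Step 1: stratum hazard ratio implied by the assumed risks.** Stratum HR = ln(1 − p_high) / ln(1 − p_low).

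- 10% and 50%: 0.693/0.105 = 6.6
- 8% and 60%: 0.916/0.083 = 11.0
- 5% and 60%: 0.916/0.051 = 17.9

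**Step 2: attenuation by hand.** Take 35% of patients above 8.5% and a within-stratum HR of 0.50.

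- Placebo risks 10% and 50%: overall placebo risk = 0.65 × 0.10 + 0.35 × 0.50 = 0.240. Treated risks are 1 − 0.90^0.5 = 0.0513 and 1 − 0.50^0.5 = 0.2929, overall 0.1359. Ratio of cumulative hazards = −ln(0.8641) / −ln(0.760) = 0.1460/0.2744 = 0.53.
- Stratum HR 3 with lower-stratum risk 15%: the upper risk is 1 − 0.85³ = 0.386. Overall risks are 0.2326 and 0.1264, and the ratio is 0.1352/0.2647 = 0.51.

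So 0.50 becomes about 0.53 with a strong stratum and 0.51 with a moderate one.

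**Step 3: power by simulation** (118 v 118, arms balanced within stratum, two-sided 5%).

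| Placebo risk, lower / upper stratum | Share >8.5% | Stratum HR | True HR | Treatment-only power | Stratified power | Loss (points) |
|---|---|---|---|---|---|---|
| 15% / 28% | 35% | 2 | 0.50 | 49.4% | 50.4% | 1.0 |
| 15% / 39% | 35% | 3 | 0.50 | 57.0% | 58.9% | 1.9 |
| 6% / 17% | 35% | 3 | 0.50 | 24.1% | 25.4% | 1.3 |
| 10% / 50% | 35% | 6.6 | 0.50 | 54% | 61% | 7 |
| 8% / 60% | 25% | 11.0 | 0.50 | 42% | 57% | 15 |
| 5% / 60% | 35% | 17.9 | 0.40 | 71% | 83% | 12 |

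Estimated HRs, treatment-only against stratified, were 0.52 and 0.49 in the fourth row and 0.45 and 0.39 in the last.

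A second grid used 15% other censoring, 30% above 8.5%, HR 0.40 and overall placebo rescue of 15%, 25% and 35%. The losses, in that order, were:

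- stratum HR 3: 1.5, 2.4 and 1.7 points
- stratum HR 6: 3.9, 5.9 and 5.8 points
- stratum HR 10: 5.3, 10.3 and 11.1 points

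At a treatment HR of 0.20 (stratum HR 6, placebo rescue 25%) power was 98.9% against 99.1%.

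**Step 4: standard error and type 1 error when the true HR is 1.**

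| Setting | Treatment-only model SE | Its sampling SD | Type 1 error | Stratified type 1 error |
|---|---|---|---|---|
| 10% / 50%, 35% above | 0.269 | 0.241 | 2.8% | 4.2% |
| Second grid, stratum HR 3 | 0.230 | 0.228 | 4.7% | 6.0% |
| Second grid, stratum HR 6 | 0.230 | 0.200 | 2.5% | 5.6% |
| Second grid, stratum HR 10 | 0.229 | 0.185 | 1.8% | 5.7% |

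The second grid used 1,500 runs, so simulation error on a 5% rate is √(0.05 × 0.95/1500) = 0.6 points.

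**Step 5: does stratifying shrink the reported standard error?** No. With 10%/50% the mean model SE was 0.269 for both models at HR 1, and 0.319 (treatment-only) against 0.320 (stratified) at HR 0.50. In the second grid the stratified SE was the larger in at least 98% of simulated trials.

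**The case against.** A reader might infer that the interval is too wide and that stratifying would tighten it. Step 5 shows otherwise: in a Cox model, conditioning on a prognostic factor leaves the standard error of the log HR about the same or slightly larger. What changes is the estimate, which moves away from 1. The treatment-only standard error is too large only relative to that estimator's own sampling SD.

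A reader might also infer that rescue simply reuses the randomisation cut. It does so in part: the HbA1c route applies by and after Week 24, is ≥8.5% where the stratum is >8.5%, and runs alongside fasting glucose limits. How prognostic the category is cannot be read from the documents, and constant-hazard simulations do not model the Week 24 start. A moderate stratum effect is as compatible with the text as a strong one, and the loss is then only 0-3 points.

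Further points on the other side stand. The SAP is silent on adjustment; it does not exclude it. The marginal HR is a legitimate estimate of a different quantity. The endpoint is a safety objective with no stated power and no multiplicity control (SAP 6.6), and a conservative test creates no false-positive risk. The factors are not universal among safety models either: the general event-rate model in SAP 6.13 names treatment only.

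Sparse data also matter. With about 13 events, stratifying by HbA1c category alone did no harm (power 25% treatment-only, 29% stratified), but stratifying on several factors could. None of this argues against stratifying by the one relevant factor.

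**Conclusion.** The point holds as a minor, free improvement. The time-to-rescue Cox model, read literally, is unadjusted, and SAP 6.3 does not reach it. If baseline HbA1c category is strongly prognostic, the treatment-only HR is attenuated relative to the within-stratum HR, the test runs at about 2-3% instead of 5%, and power falls.

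The loss is about 0-3 points at a stratum HR of 2-3. It is about 7-15 points in the scenarios with stratum HRs of 7-18, and about 4-11 points in the second grid at stratum HRs of 6-10, where it is smallest when rescue is uncommon. There is little or no loss if the treatment effect is very large. These sizes rest on assumed rescue rates, stratum shares and constant hazards; the direction does not depend on the particular values.

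The documents do not support the stronger readings that the primary or key secondary conclusions are affected, that the treatment-only HR is invalid, or that every Cox model in SAP 6.13 needs this stratum. The 8.5% argument is specific to rescue.

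**What to change.** In SAP 6.13.2.2, state that the Cox model for time to rescue is stratified by baseline HbA1c category (≤8.5%, >8.5%), taken from the clinical database as SAP 6.3 does for stratification factors, and that the p-value comes from the stratified test. Add that past OAM use and pooled country enter only if the number of events allows, since the model may run on as few as ten. Justify the choice by consistency with the randomisation and by attenuation and power, not by a narrower interval. The treatment-only HR can be kept as a descriptive marginal estimate.

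The cost is one or two sentences and one strata statement in the program, with no new data. It should be settled before unblinding.

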6.13.2.3. Pancreatitis

If data warrants, summaries of adjudicated and investigator-reported pancreatic events will be provided by treatment. Determination of investigator-reported events will be through the pre-defined SMQ search for acute pancreatitis and MedDRA PT of pancreatitis chronic. Detailed searching criteria can be found in [Appendix 2](#). Treatment-emergent adjudication-confirmed pancreatitis will be considered as AESI.

6.13.2.3.1. Pancreatic Enzyme Assessment

Observed pancreatic enzyme data (p-amylase and lipase) will be summarized by treatment and nominal visit. The number and proportion of patients with maximum postbaseline pancreatic enzyme values exceeding the following thresholds will be provided by maximum baseline pancreatic enzyme value ($\leq 1 \times$ upper limit of normal [ULN], $> 1 \times$ ULN), and treatment: $\leq 1 \times$ ULN, (> 1 to $\leq 3 \times$ ULN, (> 3 to $\leq 5 \times$ ULN, (> 5 to $\leq 10 \times$ ULN, $> 10 \times$ ULN.

An MMRM analysis will be used to analyze each pancreatic enzyme with a log transformed (postbaseline measure/baseline measure) response variable and stratification factors, treatment, nominal visit, and treatment-by-nominal visit interaction as fixed effects, and baseline value as a covariate.

6.13.2.4. Thyroid Malignancies and C-Cell Hyperplasia

Treatment-emergent thyroid malignancies and C-cell hyperplasia, will be identified using pre-defined MedDRA High Level Terms (HLTs) of thyroid neoplasms malignant, and PT of thyroid C-cell hyperplasia. Detailed searching criteria can be found in [Appendix 2](#). A summary by treatment and PT/PT within SMQ and HLT will be provided. Thyroid malignancies and C-cell hyperplasia will be considered as AESI.

6.13.2.5. Malignancy

The AE database will be searched using pre-defined SMQs to identify events consistent with malignancy. Detailed searching criteria can be found in [Appendix 2](#). A summary by treatment and PT within SMQ and a listing of TEAEs will be provided. Malignancy will be considered as AESI.

6.13.2.6. Calcitonin

Observed calcitonin data will be summarized by treatment and nominal visit. Additionally, the number and proportion of patients with a maximum postbaseline calcitonin value exceeding the following thresholds will be provided by treatment and maximum baseline calcitonin value (≤ 20 ng/L, > 20 ng/L to ≤ 35 ng/L, > 35 ng/L): ≤ 20 ng/L, > 20 ng/L to ≤ 35 ng/L, > 35 ng/L to ≤ 50 ng/L, > 50 ng/L to ≤ 100 ng/L, > 100 ng/L.

6.13.2.7. Major Adverse Cardiovascular Events

Major adverse cardiovascular events (MACE) reported by investigators are adjudicated by an independent CEC in a blinded fashion. The MACE events of special interest include: deaths due to cardiovascular cause, myocardial infarction, hospitalization for unstable angina, hospitalization for heart failure, coronary interventions (such as coronary artery bypass graft [CABG] or percutaneous coronary intervention [PCI]); and cerebrovascular events, including cerebrovascular accident (stroke) and transient ischemic attack (TIA).

A listing of patients reporting MACE events, either reported by investigator or identified by the CEC, will be provided. The listing will include treatment, patient identification including the site number, date of event, type of event as reported by the investigator, type of event as adjudicated by the CEC, time from first dose of study drug to the event, and time from last dose to the event (if patient has discontinued study drug prior to the event). Only positively adjudicated MACE will be considered as AESI.

6.13.2.8. Supraventricular Arrhythmias and Cardiac Conduction Disorders

The AE database will be searched using pre-defined SMQ or MedDRA HLT to identify events consistent with supraventricular arrhythmias and cardiac conduction disorders. Detailed searching criteria can be found in [Appendix 2](#). Incidence of the resulting TEAEs will be summarized by treatment and PT within SMQ and HLT. Treatment-emergent severe/serious supraventricular arrhythmias and cardiac conduction disorders will be considered as AESI.

6.13.2.9. Hypersensitivity Events

Hypersensitivity reactions and related information reported via the “Hypersensitivity and Anaphylactic Reactions” electronic case report form (eCRF) will be summarized by treatment. Two main analyses are performed:

- **Potential Immediate Hypersensitivity:** Analysis of TEAEs occurring from the start of study drug administration up to 24 hours after the end of study drug administration. For events without the hypersensitivity eCRF, only date (no time) information are collected, the events occurred on the same date as the study drug injection date will be included.
- **Potential Non-Immediate Hypersensitivity:** Analysis of TEAEs occurring more than 24 hours after the end of study drug administration, but prior to subsequent study drug administration.

Summaries of all potential hypersensitivity reactions will be generated by PT with decreasing frequency by treatment. The AE database will be searched using pre-defined SMQs to identify events consistent with hypersensitivity events. Detailed searching criteria for hypersensitivity

events can be found in [Appendix 2](#). Severe/serious hypersensitivity events identified by pre-defined SMQ search will be considered as AESIs.

6.13.2.10. Injection Site Reactions

Injection site reactions, incidence, and related information reported via the “Injection Site Reactions” eCRF will be summarized by treatment. Information to be summarized includes the timing of the reaction relative to study drug administration, and characteristics of the injection site reaction: erythema, induration, pain, pruritus and edema.

Additionally, potential injection site reactions will be searched by pre-defined MedDRA HLTs of injection site reactions, administration site reactions, and infusion related reactions. Detailed searching criteria for injection site reaction events can be found in [Appendix 2](#). The PT will be used for summary by treatment within each HLT category. Only the severe/serious injection site reactions will be considered as AESI.

6.13.2.11. Diabetic Retinopathy Complications

Results of the baseline dilated fundoscopic exam will be summarized by treatment. Any TEAE suspected of worsening retinopathy triggers a follow-up dilated fundoscopic exam. A summary of TEAEs suspected of worsening retinopathy and a summary of the results of the follow-up dilated fundoscopic exam will be summarized by treatment and PT. The cases with repeated fundoscopy during the course of the trial, based on clinical suspicion of worsening retinopathy that have either findings of de novo retinopathy or progression of retinopathy, and severe/serious adverse events from the PTs defined in searching criteria in [Appendix 2](#) will be considered as AESI and summarized.

6.13.2.12. Hepatobiliary Safety

6.13.2.12.1. Hepatobiliary Disorders

The AE database will be searched using SMQs to identify events consistent with hepatobiliary disorders. Detailed searching criteria can be found in [Appendix 2](#). A summary by treatment and PT within SMQ will be provided. Severe/serious hepatobiliary disorders will be considered as AESI.

6.13.2.12.2. Acute Gallbladder Disease

The AE database will be searched using pre-defined SMQs to identify events consistent with acute gallbladder diseases. Detailed searching criteria for these AEs can be found in [Appendix 2](#). A summary by treatment and PT within SMQ will be provided. Severe/serious acute gallbladder diseases will be considered as AESI.

6.13.2.12.3. Liver Enzymes

Analyses for laboratory analyte measurements are described in Section [6.13.5](#). This section describes additional analyses of liver enzymes. In addition, the following will be provided by treatment group:

- A shift table of maximum to maximum alanine aminotransferase (ALT) measurement from baseline ($\leq 1 \times \text{ULN}$, $> 1 \times \text{ULN}$) to postbaseline with the following categories: $\leq 1 \times \text{ULN}$, > 1 to $< 3 \times \text{ULN}$, ≥ 3 to $< 5 \times \text{ULN}$, ≥ 5 to $< 10 \times \text{ULN}$, $\geq 10 \times \text{ULN}$.

- A shift table of maximum to maximum aspartate transaminase (AST) measurement from baseline ($\leq 1 \times \text{ULN}$, $> 1 \times \text{ULN}$) to postbaseline with the following categories: $\leq 1 \times \text{ULN}$, > 1 to $< 3 \times \text{ULN}$, ≥ 3 to $< 5 \times \text{ULN}$, ≥ 5 to $< 10 \times \text{ULN}$, $\geq 10 \times \text{ULN}$.
- Shift tables of maximum to maximum total bilirubin and direct bilirubin from baseline to postbaseline with the following categories: $\leq 1 \times \text{ULN}$, > 1 to $< 2 \times \text{ULN}$, $\geq 2 \times \text{ULN}$.
- Shift tables of serum alkaline phosphatase (ALP) from baseline to postbaseline with the following categories: $\leq 1 \times \text{ULN}$, > 1 to $< 2 \times \text{ULN}$, $\geq 2 \times \text{ULN}$.

Maximum baseline will be the maximum non-missing observation in the baseline period. The maximum postbaseline value will be the maximum non-missing value from the postbaseline period. Planned and unplanned measurements will be included.

